1.1.3 Requirements for the proportion of recruited subjects

In order to increase the homogeneity of study subjects, study subjects can be recruited with reference to the following gender and age requirements:

① 20% male, 80% female; ② 30%-35% aged 60-65 years, ③ 30%-35% aged 66-70 years, ④ 30%-35% aged 71-75 years, ⑤ less than 10% aged 76-80 years.

(2) Sample size estimation

After scientific calculations, combined with the actual work, a total of 888 people are needed for this project, then each group needs a sample size of $n=111$, and a total of 37 people are recruited in each street (town). The sample size calculation process is as follows:

This study uses the dichotomous variable "whether a fall occurs" as the outcome indicator. According to the results of the occurrence of falls among the elderly in the community in Guangzhou City in 2023, the incidence of falls among the elderly in Baiyun District was 17%. After discussion with experts, it was concluded that a 35% reduction in the incidence of falls after the intervention was considered to be of public health significance. In this study, the test level was set at $\alpha=0.05$ and the test efficacy at 0.8 (i.e., $\beta=0.2$). The proposed factorial design for this study is based on the sample size formula (below) for factorial designs in which the outcome variable is a dichotomous variable, and the sample size required for each test condition can be obtained as:

$$n = \frac{(Z_{1-\alpha/2} + Z_{1-\beta})^2}{2^k [\arcsin(\sqrt{\frac{\rho+\rho\delta}{2}}) - \arcsin(\sqrt{\frac{\rho-\rho\delta}{2}})]^2} \approx 83$$

$$\rho=0.17, \delta=0.35, Z_{1-\alpha/2}=1.96, Z_{1-\beta}=0.84, k=3.$$

The total sample size required for the 8 test conditions was:

$$N_{\text{conditions}} = 83 \times 8 = 664$$

According to S. Bhasin, T.M et al, the design effect of whole cluster randomisation can be obtained by estimating $ICC = 0.0076$ and mean number of individuals in the cluster $m = 28$:

$$DE = 1 + (m-1) \times ICC = 1 + (28-1) \times 0.0076 = 1.2052$$

The sample size was set to be the same for the eight test conditions, and the total sample size required for the study was:

$$N = N_{\text{conditions}} \times DE \div (1 - 10\%) \approx 888$$

The required sample size for each test condition was then 111 cases;

Each of the 24 streets recruited 37 study participants.

(3) Intervention groups

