3.1.2 Assessment period

From May 2024 to May 2025, information on the occurrence of falls was collected on a monthly basis during the period from the start of the intervention to the completion of 12 months of the intervention.

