SPSS20.0 was used for statistical processing. Variables such as general demographic characteristics, disease characteristics, previous falls, and level of social support at baseline were compared to see if there were any differences between the different intervention groups, and variables with differences would be corrected in the subsequent analyses. Intent-to-treat (ITT) analysis is proposed to evaluate the intervention in this study. Descriptive analysis: statistical descriptions of primary outcome variables, secondary outcome variables, intervention implementation and other synergistic factors, etc., and independent samples t-tests (continuous variables such as Older Adult Falls Efficacy Scale scores, Quality of Life Scale scores, Older Adults' Falls Knowledge and Belief Behaviour Scale scores, etc.) and chi-square tests (categorical variables such as attitudes towards the intervention strategy, incidence of falls, etc.) to compare the between-groups differences were used.

The study proposes to assess the economic benefits using Incremental Cost-Effectiveness Ratio (ICER), which is the increased cost per unit of effect.

VIII. Safety Guarantee

- (1) When carrying out the various screening, assessment, training, exercise and other activities of the project, the safety and physical health of the research subjects should be ensured as the first principle.
- (2) During the various screening and assessment processes, research subjects should be clearly informed of the testing methods and possible risks. The project may conduct demonstrations and allow research subjects to practise before taking formal measurements. The staff should remind the participants that they should not pursue "good results" in the test.
- (3) In the process of training and exercise, the basic principles are gradual and according to one's ability, and research subjects should not be forced to perform movements that are beyond their ability. All exercises are subject to the subjective feeling of the research subjects themselves, while attention should be paid to correcting the research subjects' sense of "not obeying the old" and stopping dangerous actions in time.

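### Falls are recorded monthly for a year, but the only named test is a yes/no chi-square that uses neither timing, part-year follow-up nor repeat falls, and no rule covers incomplete years

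*Combined protocol and SAP*

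**What the plan says.** **Endpoint.** Section III (2) sizes the trial on a binary outcome: "This study uses the dichotomous variable 'whether a fall occurs' as the outcome indicator".

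**Data.** Section VI (3) 3.1.2 states that "information on the occurrence of falls was collected on a monthly basis" from the start of the intervention to 12 months. Under 3.1.4, participants keep a monthly calendar, staff collect it each month, and a questionnaire follows up the time of any fall. Under 3.3.3, the 12-month survey omits the falls section, so the calendar is the source for the year.

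**Test.** Section VII (2) lists, under descriptive analysis, "chi-square tests (categorical variables such as attitudes towards the intervention strategy, incidence of falls, etc". No time-to-event, person-time or count method is named. The same paragraph proposes intention-to-treat and says that variables differing at baseline will be corrected for later, without naming a model.

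**Incomplete years.** Section III (2) inflates the sample for 10% loss. Section IX (4) 4.1 counts as lost those who refuse further intervention and those who withdraw for adverse health outcomes such as hospitalisation for illness. Section IX (4) 4.3 asks that reasons be recorded and that effects be evaluated where circumstances allow. Nothing says how a person with seven months of calendars enters the fall comparison.

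**The concern.** The trial pays for month-level data and then names a test that collapses it to one binary value per person. Two different things are at stake, and which one applies depends on how incomplete years are handled.

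- If people with incomplete years are dropped, their observed months and first falls are lost. The cost is precision.
- If they are kept and coded as no fall, or kept only when they are known to have fallen, the comparison is distorted when loss differs between conditions.

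With no rule set in advance, that choice on the primary outcome falls to whoever cleans the data. Repeat falls count for nothing in the yes/no test under any coding.

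**Working it through.** **Inputs from Section III (2).** "the incidence of falls among the elderly in Baiyun District was 17"% (taken as a 12-month risk; the period is not stated). "a 35% reduction in the incidence of falls after the intervention was considered to be of public health significance", so 0.17 × 0.65 = 0.1105. "the test level was set at $\alpha=0.05$ and the test efficacy at 0.8", two-sided ("Z_{1-\alpha/2}=1.96"). Loss 10%, design effect 1.2052. "The required sample size for each test condition was then 111 cases", so each main effect compares 4 × 111 = 444 people with 444.

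**Assumed, not in the documents.** Constant fall hazard; loss uniform over the year; negative binomial dispersion k from 0 to 3; unequal loss of 15% against 5% in step 4.

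**1. The plan's own figure.** n = (1.96 + 0.84)² / {8 × [arcsin√0.11475 − arcsin√0.05525]²} = 83.5 (printed 83). Then 83 × 8 = 664, and 664 × 1.2052 / 0.9 = 889.2 (printed 888). The formula as printed contrasts 11.5% with 5.5%, not 17% with 11.05%. That is a separate point, but it explains why the powers below start near 60% and not 80%; the choice of test does not.

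**2. Chi-square on completers.** Effective n per level = 444 × 0.9 / 1.2052 = 331.6. Mean risk = 0.14025.

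z = [0.0595 × √331.6 − 1.96 × √(2 × 0.14025 × 0.85975)] / √(0.17 × 0.83 + 0.1105 × 0.8895) = (1.083 − 0.963) / 0.489 = 0.247. Power 59.8%.

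**3. Time to first fall, all follow-up used.** Hazard ratio = ln(0.8895) / ln(0.83) = 0.1171 / 0.1863 = 0.628.

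Chance of a fall before a uniform drop-out time = 1 − p / [−ln(1 − p)]: 8.76% at p = 0.17 and 5.63% at p = 0.1105. Observed first-fall proportions: 0.9 × 0.17 + 0.1 × 0.0876 = 0.1618, and 0.9 × 0.1105 + 0.1 × 0.0563 = 0.1051.

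Effective events = (444 / 1.2052) × (0.1618 + 0.1051) = 98.3. By the Schoenfeld formula, z = 0.4645 × √(98.3 / 4) − 1.96 = 0.343. Power 63.4%.

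First falls used: 0.2669 / 0.2805 = 95%, against 90% for completers.

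| Loss | Chi-square, completers | Time to first fall |
|---|---|---|
| 0% | 64.3% | 65.6% |
| 10% | 59.8% | 63.4% |
| 20% | 54.8% | 61.1% |
| 30% | 49.4% | 58.8% |

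About 1.3 of the 3.6 points at 10% loss are present with no loss at all; the rest comes from part-year follow-up. Coding drop-outs without a recorded fall as non-fallers gives 61.9% at 10% loss.

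**4. Coding bias, no true effect (17% in both levels), loss 15% against 5%.**

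- Incomplete coded as no fall: (0.85 × 0.17 + 0.15 × 0.0876) / (0.95 × 0.17 + 0.05 × 0.0876) = 0.1576 / 0.1659 = 0.95.
- Completers plus known early fallers: [0.1576 / (0.85 + 0.15 × 0.0876)] / [0.1659 / (0.95 + 0.05 × 0.0876)] = 0.1826 / 0.1738 = 1.05.
- Completers only: 0.17 / 0.17 = 1.00 if loss is unrelated to falling.

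With equal 10% loss and the planned effect, the two codings give risk ratios of 0.650 and 0.652, so the relative effect is essentially unharmed.

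**5. Number of falls.** With risks held at 17% and 11.05%, mean falls are [(1 − p)^(−k) − 1] / k. For k from 0 to 3, repeat falls are 8% to 28% of all falls. With 400 per level and the design effect, a negative binomial analysis has 62% to 72% power. Part of that gain is a larger effect: the implied rate ratio moves from 0.63 to 0.56. With the rate ratio held at 0.65 (10% loss, no design effect), power is 66.9% falling to 59.8% as k rises, against 62.0% falling to 45.3% for the completers chi-square.

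**The case against.** A reader might infer that the plan forces a biased coding. It does not: no coding is prescribed, and dropping incomplete years is unbiased if loss is unrelated to falling. Nor do the two harms add up. First falls are lost only if incomplete people are dropped, and the computed distortion arises only if they are kept.

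The distortion is also modest. In step 4 the no-fall coding shifts the risk difference by 0.0082 against a standard error of √[(0.1576 × 0.8424 + 0.1659 × 0.8341) / 444] = 0.0247, or z of 0.33. Type I error would rise from 5% to about 6.3% before clustering. The documents do not predict unequal loss, and they plan telephone checks of missing values and at least monthly contact. Unequal loss is plausible, though: refusing further intervention counts as loss, and Group 5 is offered none while Group 1 is offered all three components.

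The chi-square sits under descriptive analysis, and the promised baseline correction implies some further model. Any fall is a legitimate endpoint and the one sized on. Both points stand, but an unnamed model does not settle how incomplete years are treated.

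Repeat falls are not wholly unused, since fall-related costs are collected by fall and can enter the economic evaluation. The indicator list in Section VI (1) 1.2.6 is garbled, so a count indicator may have been lost there. Whether the interview yields counts depends on Annex 5 Part III, which is not available.

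Finally, a time-at-risk model does not remove bias from withdrawal for illness.

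**Conclusion.** The point holds as a gap in method and in rules. The plan names no analysis that uses fall timing, part-year follow-up or repeat falls, and it does not say how an incomplete year is handled. At the planned 10% loss the precision at stake is about 3.6 power points (59.8% against 63.4%), widening to about 9 points at 30% loss. The possible distortion is a false risk ratio of about 0.95 or 1.05, and only under two of the possible codings with unequal loss.

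These sizes rest on 17% being a 12-month risk, a constant hazard, uniform loss and the plan's design effect. The 15% against 5% loss and the dispersion range are illustrations. The documents do not support saying that bias is built in, or that a time-at-risk model would cure every form of it. The change is still worth making: it is cheap, uses data already being collected and removes an open choice on the primary outcome.

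**What to change.** 1. Keep any fall in 12 months as the endpoint. Replace the chi-square with a person-month complementary log-log model for first fall, with the three component terms, and report model-based 12-month risks beside the hazard ratios.
2. Censor at the last month with known fall status, and define what makes a month known (calendar returned, or status confirmed at the monthly contact). Report months observed and reasons for loss by condition.
3. Allow for street by a random effect or street-level cluster-robust errors, with a small-sample correction for 24 streets. Do not use fixed street effects: each condition consists of whole streets (Section III (3)), so they would be aliased with the components.
4. Add number of falls as a secondary outcome where the fall interview gives counts: negative binomial, offset log months observed, same treatment of street.
5. Add a sensitivity analysis for health-related withdrawals (Section IX (4) 4.1), for example imputing the unobserved months with the fall hazard raised over a stated range. The main model assumes that loss is unrelated to falling given its terms.

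The cost is SAP wording, fixed before unblinding, and a check that the named software fits these models; no new data on first falls are needed. The downside is that hazard and rate ratios are less familiar, which is why the 12-month risks are reported beside them.

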2.1 Unify tools and methods

Unify survey, measurement and assessment methods and tools.

2.2 Training

Conduct unified training and assessment for researchers participating in data collection regarding the use of work programmes, techniques and tools related to assessment information collection. They will be allowed to work only after passing the assessment.

2.3 On-site verification of data collection

All surveys, measurements and assessment work must be carried out at the site for corresponding verification and quality control. Mainly includes on-site verification of questionnaires and measurement items. Some of the research subjects are taken to repeat

the measurements. For details of the specific methods, please refer to the Requirements for On-site Quality Control Work of Survey and Evaluation (Annex 15).

2.4 Data entry and cleaning

According to the questionnaire or form, create and use REDCap to establish a unified entry file and set up preliminary logical calibration. Randomly select more than 20% of the entered questionnaires for secondary calibration to ensure the quality of data entry. Establish uniform data cleaning regulations and document the data cleaning process.

(3) Quality control of the implementation of intervention group activities

3.1 Unify the content, methods and tools of group activities.

Develop a unified programme of group activities and use unified training manuals and tools.

3.2 Training and evaluation of group activity implementers

Organise certified training of trainers (team leaders and assistants) to implement intervention group activities. They will pass the unified standardised training, practice and assessment, and will only be allowed to work after passing the assessment.

3.3 On-site evaluation of the quality of intervention group activities

On-site evaluation teams from CDC agencies at the city and district levels conduct on-site quality assessment of group activities. See the process evaluation section for details.

(4) Management of lost visitors

4.1 Definition of lost visitors:

Lost visitors were defined in this study as 1) study participants who explicitly refused to continue with the intervention via text message, WeChat applet, or phone call; and 2) withdrawal from the study due to the occurrence of an adverse health outcome, including hospitalisation for somatic or psychological illnesses, etc. Hospitalisation of study subjects due to unintentional injuries was not used as a criterion for study subject withdrawal from the study, but was recorded as a health outcome.

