3.1 Data collection on the occurrence of falls in the study population

3.1.1 Assessment subjects

All study subjects in the 8 study groups.

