4.3 Management of lost visitors

In the event of a missed visit, the reasons for the participant's withdrawal from the study will be recorded in detail in the "Record of Participation of Research Subjects in the Project Process" (Attachment 3), and an evaluation of the effectiveness of the project will be carried out as far as possible according to the actual situation.

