4.4. Monthly Reporting System of Research Subjects' Information

Report the participation of research subjects in intervention activities and loss of visits in the four research groups on a monthly basis.

(5) Control of pollution

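### Loss to follow-up is defined by refusing the intervention or withdrawing through illness, not by missing fall data, and this is not reconciled with the ITT analysis

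*Combined protocol and SAP*

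**What the plan says.** Section IX (4) 4.1 gives two ways to become a lost visitor. The first is to be among "study participants who explicitly refused to continue with the intervention via text message, WeChat applet, or phone call". The second is "withdrawal from the study due to the occurrence of an adverse health outcome, including hospitalisation for somatic or psychological illnesses". The section then adds an exemption: "Hospitalisation of study subjects due to unintentional injuries was not used as a criterion for study subject withdrawal from the study"; such admissions are recorded as a health outcome instead.

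Other parts of the plan bear on the same people:

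- VII (2), Data collation and analysis: "Intent-to-treat (ITT) analysis is proposed to evaluate the intervention in this study". It gives no analysis set and no rule for missing outcomes.
- VI (3) 3.1.1, on who provides fall data: "All study subjects in the 8 study groups". Sections 3.2.1 and 3.3.1 set the same scope for the 6- and 12-month assessments.
- IX (4) 4.3, on what follows a loss: the reason for withdrawing from the study is recorded, and "an evaluation of the effectiveness of the project will be carried out as far as possible according to the actual situation".
- IX (4) 4.4 requires reporting of "loss of visits in the four research groups on a monthly basis", whereas Table 1 has eight groups.

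**The concern.** A definition of loss should say whose outcome is unknown. This one says who stopped the intervention or withdrew through illness. Someone who declines further sessions but still returns every fall calendar is lost under 4.1. Someone who silently stops returning calendars meets neither criterion, and someone who dies does so only if the death is handled as a health-related withdrawal. Because the exemption covers injury admissions only, it implies that admission for illness is a ground for leaving the study.

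If staff act on the rule as written, calendars and assessments may stop for people whose outcomes ITT needs. Two consequences follow:

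- Group 5 receives no component, Group 8 has one home visit, and Groups 1 to 4, 6 and 7 have four dated sessions. On the literal reading the chance to be classed as lost by refusal therefore varies with allocation.
- The illness criterion can operate in every group, and it may remove frailer people throughout.

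The loss count itself also stops being a usable measure of how complete the outcome data are.

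**Working it through.** **The plan's own figure.** III (2) states 83 per condition, so 83 × 8 = 664. The design effect is 1 + 27 × 0.0076 = 1.2052, and 664 × 1.2052 / 0.90 = 889.2. The plan states 888 (8 × 111), so the figure reproduces to rounding. The 10% divisor is not labelled; reading it as a loss allowance is an assumption.

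**Inputs for the illustration.** Taken from III (2): fall risk 17% and a 35% relative reduction, so the target is 0.35 × 17 = 5.95 points; 111 people per group. Assumed: no true effect; L = 10% of each component group deleted completely, including calendars already returned; nobody deleted in Group 5; those deleted have R = 1.25, 1.5 or 2 times the average risk.

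**Step 1: one component group against Group 5.** Remaining risk = 0.17 × (1 − L × R) / (1 − L).

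- R = 1.25: 0.17 × 0.875 / 0.9 = 16.53%, a spurious reduction of 0.47 points
- R = 1.5: 0.17 × 0.85 / 0.9 = 16.06%, 0.94 points
- R = 2: 0.17 × 0.80 / 0.9 = 15.11%, 1.89 points

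Divided by 5.95, these are 8%, 16% and 32% of the target.

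**Step 2: a factor main effect.** Take education. The Yes level is Groups 1 to 4, all with 10% deleted. The No level is Groups 5 to 8, three of which also have 10% deleted. The share of the remaining No level that comes from Group 5 is 111 / (111 + 3 × 99.9) = 0.270. The spurious main effect is therefore 0.270 times the Step 1 difference. The same holds for exercise and environment, since Group 5 sits in the No level of each.

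| R | Against Group 5 (points) | Main effect (points) | Main effect as share of 5.95 |
|---|---|---|---|
| 1.25 | 0.47 | 0.13 | 2% |
| 1.5 | 0.94 | 0.26 | 4% |
| 2 | 1.89 | 0.51 | 9% |

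**Step 3: if Group 8 also loses nobody by refusal.** Environment Yes (Groups 1, 3, 6, 8) and No (Groups 2, 4, 5, 7) then each hold three groups with deletion and one without, so the spurious environment effect is zero. For education and exercise the No level now holds two intact groups. Their share is 222 / (222 + 2 × 99.9) = 0.526, and the main effect becomes 0.526 × 0.47, 0.94 or 1.89 = 0.25, 0.50 or 0.99 points (4%, 8% or 17% of target).

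**Which contrast applies.** VII (2) plans t-tests and chi-square tests of differences between groups, and II (1) plans an economic comparison of the intervention groups. The plan does not limit itself to main effects, so both contrasts are shown.

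**The case against.** The strongest reply is that nothing in the plan says lost participants, or the falls they have already reported, leave the analysis. Section 4.3 keeps evaluating them where it can. Fall data are to be collected from everyone, 4.2.2 requires contact at least monthly, and 4.2.3 requires absentees to be traced. All of this is compatible with ITT if it is carried out. This stands: a reader might infer that the plan contradicts ITT, and the documents do not support that. They leave the matter unsettled, because 4.3 makes continued evaluation depend on circumstances and VII (2) supplies no rule.

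A reader might also infer that people are removed from treated levels only, and that every main effect is biased by 8% to 32% of the target. Neither follows. Illness withdrawal can occur in all eight groups, and injury admissions, the ones closest to falls, are exempt. The 8% to 32% range belongs to a comparison with Group 5; each factor's No level contains three groups that also receive a component.

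Two further points stand in part. The plan uses the word intervention loosely: VI (3) 3.1.2 speaks of completing 12 months of it, although II (2) describes a 2-month intervention. The refusal criterion may therefore mean refusing the project, which Group 5 members could also do. And no document says that refusers fall more often. If fitter people decline, the sign reverses.

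**Conclusion.** The concern holds in a limited form. Section 4.1 defines loss by intervention refusal and health-related withdrawal, not by missing fall data, and it is not reconciled with ITT or with fall follow-up of all participants. On the literal reading, recorded loss can depend on allocation through the refusal criterion, because Group 5 has nothing to refuse.

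Under the assumptions above, the effect is moderate for a comparison with Group 5 and small for a main effect when all seven component groups lose equally. It vanishes for environment, and roughly doubles for education and exercise, if Group 8 loses nobody by refusal. These are illustrations of complete deletion, which the plan does not prescribe. They are not estimates of bias in this trial, and the direction depends on who refuses. What is certain is narrower: as written, two teams could apply the rule and obtain different loss counts and different ITT sets.

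**What to change.** 1. In IX (4) 4.1, record refusal of sessions or visits separately from loss to follow-up. State that neither refusal of the intervention nor hospital admission for illness by itself ends the monthly fall calendars or the 6- and 12-month assessments. This concerns data collection only and sets no rule on who continues the sessions.
2. Define loss to follow-up as withdrawal of consent to data collection, death, or no further contact.
3. In VII (2), state that everyone is analysed in the allocated condition and that any fall recorded before loss counts in the binary outcome. State how people lost without a recorded fall are handled, since dropping them while keeping those lost after a fall would overstate risk. Add a missing-outcome sensitivity analysis that varies their assumed risk by group, both above and below average.
4. Reconcile 4.1, 4.3 and VII (2), and correct 4.4 so that loss is reported for all eight groups.

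The cost is protocol wording and slightly more follow-up, within the monthly contact already planned in 4.2.2. The total of 888 does not change.
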